**1. PURPOSE AND BACKGROUND**

Atopic Dermatitis (AD) is the most common inflammatory skin disease, affecting about 17% of children and 6% adults in the USAi, ii. AD is characterized by skin barrier disruption, an aberrant adaptive immune response (*i.e.*, Th2 polarized) to environmental allergens, susceptibility to cutaneous bacterial infections and intractable itchiii, iv. The intense pruritus and cutaneous infections contribute to the morbidity of AD and are major drivers of the reduced quality-of-life associated with this diseasev, vi. In the World Health Organization 2010 Global Burden of Disease survey, AD has ranked first among common skin diseasesvii. So far, AD treatments have targeted inflammation with the widespread use of topical and more intermittent use of systemic corticosteroids. In summary, despite its high prevalence, effects on quality-of-life and economic burden – there are few effective treatments for AD.

Doxycycline are tetracycline antibiotics broadly used systemically to treat inflammatory-dermatologic conditions. Several studies in human and animal models have shown doxycycline have anti-inflammatory and pro-healing properties, mainly by blocking tissue proteolytic activity. Doxycycline have been reported to nonselectively inhibit members of the metalloproteinases (MMP) superfamily [reviewed in viii, ix]. In addition to this direct inhibitory activity, doxycycline indirectly prevents tryptic kallikreins activation by MMPsx. Growing body of evidence suggests that the tetracycline might also directly downregulate Protease Activator receptor (PAR)-2 expression and function, which was also found to play a role in induction of local inflammatory

mediatorsxi. Importantly, the doxycycline antimicrobial activity could lead to reduced *Staphylococcus* infection/colonization in AD skin, a known trigger of AD flares.

Alchem Laboratories Corp has recently acquired from Nanotherapeutics, Inc the first topical formulation of doxycycline: NanoDOX® Hydrogel, a novel small particle gel suspension of doxycycline 1%. The topical 1% doxycycline monohydrate hydrogel product is available for clinical testing through a FDA-cleared IND obtained in 2008 to treat chronic skin wound and a phase 2 study to evaluate safety and efficacy completed in 2011 at VA hospital in Gainesville ("Safety Study of Topical Doxycycline Gel for Adult Diabetic Lower Extremity Ulcers", Protocol 2008-DOX-NT/003, ClinicalTrials.gov Identifier: NCT00764361). An amendment to the IND 77520 has been filed with the FDA by Alchem Lab for the new IND indication for use in AD.

Safety preclinical studies of NANODOX® were previously evaluated by Nanotherapeutics. Briefly, Franz diffusion cells were used to analyze the amount of doxycycline released out of a NanoDOX® Hydrogel or particle suspension across an exact area with respect to time. These conditions may be used to mimic an exposed wound and the resulting drug release out of the NanoDOX® Hydrogel into the body. Overall, less than 1% w/w of the 15 mg total doxycycline available in the donor chamber in the gel (11.18µg, or 0.08%) as well as the suspension (29.88µg, or 0.21% w/w) diffused across the membrane into the receptor chamber. In a rat wound healing study, NanoDOX® Hydrogel was tested at doxycycline concentrations of 0.0% (placebo hydrogel), 0.3%, 1%, and 3% w/w as well as untreated control. The results of the study demonstrated no significant differences between the histological scoring for all concentrations and the control. All concentrations were judged to be non-irritants versus the control. In humans, NanoDOX® Hydrogel treatment was evaluated in a pilot, randomized, controlled trial of chronic, diabetic, lower-extremity foot ulcers. All four chronic ulcers of diabetic patients treated daily with topical 1% NanoDOX® Hydrogel healed in the 20-week treatment period, whereas only one of three patients treated with vehicle healed (p=0.05). No adverse events were attributed to NanoDOX® Hydrogel treatment.

**Aim of this protocol is to investigate the safety and clinical efficacy of 1% topical Doxycycline Monohydrate (NanoDOX® Hydrogel) in AD.** It is our hypothesis that daily application of NanoDOX® hydrogel blocking cutaneous proteases activity in AD subjects will reduce severity of the disease, by restoring skin barrier function and reducing skin driven inflammation. Importantly, we will also monitor the anti-microbial activity of this product on AD skin, as colonization with *Staph aureus* is typically associated with disease severity. This work will likely be the first step to developing new therapeutics targeting skin proteases activity.

## 2. CHARACTERISTICS OF THE RESEARCH POPULATION

**Number of subjects** We intend to have 15, non-pregnant, non-lactating women and men of any race and ethnicity, ages 18 to 65 yrs, who are generally healthy except for atopic dermatitis diagnosed by the US Consensus criteria complete this study. This may require enrolling up to 30 subjects depending on retention rates and dropouts. Patients can have other allergic conditions such as asthma, allergic rhinitis, food allergies, etc. All AD subjects must have

moderate-severe AD as defined at screening by an Eczema Area and Severity Score (EASI)  $\geq$  10.

**Gender of subjects** We will be recruiting both male and female subjects

**Age of subjects** We will be including subjects between the ages of 18 and 65 years.

**Racial and Ethnic Origin** We will not have any restrictions based on racial or ethnic origin. We based our target research population racial and ethnic distribution on the data of the 2000 United States Census for the Alachua Area.

**Vulnerable subjects** We will not be targeting vulnerable subjects, however staff and students of UF and Shands may be enrolled as part of the general population with AD

### **Inclusion Criteria**

- Male or female, 18 through 65 years of age, inclusive who are generally healthy except for active atopic dermatitis diagnosed by the following criteria.
- **Active Atopic Dermatitis:** Subjects *must have* according to medical records, patient account or by medical exam of the investigator:
  - Pruritus
  - Eczema (acute, subacute, chronic)
  - Chronic or relapsing history

Most subjects *will have* (seen in most cases, adding support to the diagnosis):

- Early age at onset
- Atopy
- Personal and/or family history
- Xerosis

Subjects *may have* (these clinical associations help to suggest the diagnosis of AD but are too nonspecific for defining or detecting AD for research or epidemiological studies):

1. Atypical vascular responses (e.g., facial pallor, white dermographism, delayed blanch response)
  2. Keratosis pilaris/hyperlinear palms/ichthyosis
  3. Ocular/periorbital changes
  4. Other regional findings (e.g., perioral changes/periauricular lesions)
  5. Perifollicular accentuation/lichenification/prurigo lesions
- Moderate to Severe AD: clinical score based on EASI  $\geq$  10 and/or IGA 1-2.
  - If receiving antihistamines, are on a stabilized dose, and expect to maintain this dose throughout the study
  - All female subjects of childbearing potential must have a negative pregnancy test at screening visit and must be on an acceptable methods of contraception from the Screening Visit continuously until 30 days after stopping study drug.

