### Screening visit (optional):

- 1) Consenting and confirmation of inclusion & exclusion criteria
- 2) Identification of the target area to be treated with NANODOX® and digital picture of the targeted lesion. The picture will not include subjects' identifiers (e.g. facial features, tattoo, ect)
- 3) possible washout period (topical only in the chosen area – treatment and biopsy sites)
- 4) scheduling visit 1

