**Study procedures & methods**

- **Disease status assessment:** **1)** Investigator Global Assessment (IGA), which will provide information of the overall disease (four point scale: clear, mild, moderate, severe) and it is the score requested by FDA for clinical study and **2)** Eczema Area and Severity Index (EASI), a well-accepted and validated scoring system for general disease activityxiv. It is the sum of the intensity scores (0 to 3) for four signs: erythema, induration, excoriation, lichenification and it is recorded for targeted treatment areas as well as four regions of the body (i.e., head, trunk, lower and upper extremities). Data will be reported as percent change in EASI score from baseline and each visit. Proportion of participants achieving EASI50 and EASI75 will be determined at each study timepoints. The presence or absence of skin irritation (e.g. macular/papular eruption), redness, atrophy and telangiectasia will be noted at each study visit.  
**3)** The pruritus intensity will be assessed using the 5-D Pruritus Scale. The pruritus categorical scale is a 4-point scale commonly used in clinical studies of AD and has less of a “middling” effectxv The scale is rated as follows: 0: absence of pruritus; 1: mild, pruritus (occasional slight itching/scratching); 2: moderate pruritus (constant or intermittent itching/scratching that does not disturb sleep) and 3: severe pruritus (bothersome itching/scratching that disturbs sleep).
- **Digital pictures:** A digital picture will be taken with a dedicated digital camera. The pictures will be labeled with the subject’s study ID and date. Pictures will not include identifying information (e.g. facial features, tattoo, etc). Pictures will be taken at a distance for easy identification of the anatomical area and closer to better capture clinical changes. Digital photographs will be used to record the location and monitor the size of target lesions. Quantification of change in size will be obtained using Image J software.  
At conclusion of the study, two trained physicians/dermatologists will be asked to score clinical pictures (0-4 scale, clear, mild, moderate, severe) in a blind fashion (*i.e.*, pictures will be de-identified and presented randomly/ not in chronologic order). This would allow to objectively confirm the clinical score taken during the study.

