## **5. DATA ANALYSIS AND DATA MONITORING**

### **Primary Outcomes:**

1. Assessment of safety and tolerability of NanoDOX® Hydrogel in AD subjects on lesional and non-lesional (clinically normal appearing) skin, including pain and dermatologic/skin toxicity (incidence, severity, frequency, duration and causality) in lesional skin at target site (NanoDOX® Hydrogel). 2. Improvements rate of IGA and EASI score in lesional skin treated with NanoDOX® Hydrogel before and after treatment. We will quantify clinical improvement as: IGA (0-4) fold improvement from baseline; percent of subjects reaching EASI50 (50% improvement over baseline) or EASI75 (75% improvement over baseline) at each time point post treatment (V2 and V4). 3. Objective Clinical improvement based on digital photography scoring (0-4 scale and size of active lesion), measured as fold improvement over baseline at each time point (V2 and V4).

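### The two statements of the severity criterion disagree: one requires EASI of at least 10 for everyone, the other also admits an undefined IGA 1-2, which probably includes mild disease

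*Combined protocol and SAP*

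**What the plan says.** Section 2, Number of subjects, sets a condition for all subjects: "moderate-severe AD as defined at screening by an Eczema Area and Severity Score (EASI"), with a threshold of 10 or more. It offers no alternative route.

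Section 2, Inclusion Criteria, carries the moderate-to-severe label but sets the score at EASI of at least "10 and/or IGA 1-2".

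The IGA itself appears in three forms:

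- Section 3, Study procedures & methods (Disease status assessment), describes it as a "four point scale: clear, mild, moderate, severe", with no numbers attached.
- Section 5, Primary Outcomes, lists "IGA (0-4) fold improvement from baseline", a range with five values.
- The blinded photograph score (Section 3, Digital pictures), meant to confirm the clinical score, is a "0-4 scale, clear, mild, moderate, severe": four labels on five values.

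The optional screening visit and Visit 1 both include the step "Consenting and confirmation of inclusion & exclusion criteria".

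**The concern.** Staff at screening and Visit 1 confirm the inclusion and exclusion criteria, so the bulleted list is probably the rule they will apply. That list is wider than the population stated a few paragraphs earlier. A subject with EASI below 10 and IGA 1-2 is eligible under one statement and ineligible under the other, so the site and the monitor have no single rule to check against.

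The IGA route is also undefined. If the scale ascends, its grades 1 and 2 sit at the milder end, which contradicts the label the criterion carries.

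At stake is the description of the study population. This is a single-arm study with 15 planned completers, and subjects who do not meet its own severity definition could be reported as moderate-severe. Section 5 plans a table of baseline characteristics but no count by entry route.

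**Working it through.** **The plan's own figure.** Section 5 calls 6 or more EASI50 responses in 15 promising and states power of over 96% at a true response rate of 60%. The exact binomial gives P(X ≥ 6 | n = 15, p = 0.60) = 0.966, which agrees. This calculation does not use the entry rule, so the contradiction leaves it unchanged.

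**The two rules side by side.**

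| Subject | Number of subjects paragraph | Inclusion Criteria list |
|---|---|---|
| EASI ≥ 10, any IGA | meets | meets |
| EASI < 10, IGA 1-2 | fails | meets |
| EASI < 10, other IGA | fails | fails |

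The second row is the conflict. It exists whatever the IGA numbers mean. Reading the conjunction strictly as *and* does not remove it, because the list would then add an IGA condition that the paragraph lacks. None of the exclusion criteria sets a severity floor that would catch these subjects.

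**What IGA 1-2 could mean.** Number the four labels (clear, mild, moderate, severe) consecutively and read off grades 1 and 2:

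| Coding | IGA 1 | IGA 2 | Gives moderate and severe? |
|---|---|---|---|
| Ascending 0–3 | mild | moderate | no |
| Ascending 1–4 | clear | mild | no |
| Descending 0–3 | moderate | mild | no |
| Descending 1–4 | severe | moderate | yes |

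The only numeric range printed for the IGA is 0–4, which leaves one of its five values without a label. Placing that value at each position in turn gives, for IGA 1 and IGA 2:

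| Unlabelled value | Ascending 0–4 | Descending 0–4 |
|---|---|---|
| 0 | clear, mild | severe, moderate |
| 1 | unlabelled, mild | unlabelled, moderate |
| 2 | mild, unlabelled | moderate, unlabelled |
| 3 or 4 | mild, moderate | moderate, mild |

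Every ascending coding puts mild disease in IGA 1-2 and leaves severe disease out. Only two codings make IGA 1-2 exactly moderate and severe. Both are descending, and one of them also needs a grade above severe that the protocol never mentions.

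**Direction.** No section states it. Two features of Section 3 point to ascending: both the IGA and the photograph labels are listed starting from clear, and the itch scale in the same section is numbered upwards ("0: absence of pruritus; 1: mild, pruritus (occasional slight itching/scratching); 2: moderate pruritus", then 3 for severe).

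**Size.** The protocol gives no figure for how many subjects would enter on IGA alone. Logically it could be anywhere from 0 to 15 of the 15 completers, and each one is 1/15 = 6.7% of the set.

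**Effect on the response count.** This cannot be computed, because no response rate by severity is given. It also need not be large. Treatment covers an area about the size of an index card (Section 3, Study Design), and the second primary outcome is "Improvements rate of IGA and EASI score in lesional skin treated with NanoDOX", that is, in treated lesional skin. Whole-body severity at entry need not determine response there.

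**The case against.** The strongest reply is that the mild-disease reading is an inference. Both statements carry a moderate-to-severe label, and a reader applying both would not enrol a subject judged mild. Requiring EASI of at least 10 satisfies both at once. The itch scale is a different instrument, and the photograph score, with four labels on five values, cannot fix any code. This is fair as far as it goes. The ascending direction is likely but not proven. The contradiction between the two rules does not depend on it, however, and if a descending scale was intended the text still has to say so.

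A second reply is that the consequence is small. This is an open-label proof-of-concept pilot, clinical scores are taken at Visit 1, and subjects with baseline EASI below 10 could be picked out of data already being collected. That also stands in part, and it is why the claim is confined to who is enrolled and how they are described. But the protocol does not commit to reporting that count, and finding such subjects afterwards does not tell the site whether to enrol them.

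A third reply is that the mismatch between four labels and a 0–4 range is really an outcome-measurement matter. It is used here only because it leaves IGA 1-2 without a meaning; a single scale definition would settle both.

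**Conclusion.** The concern holds. The two severity rules conflict as written, nothing elsewhere in the protocol reconciles them, and confidence in that is high. That IGA 1-2 admits mild disease is the likely reading rather than an established one; it rests on the IGA ascending, as the order of its labels suggests. The number of subjects affected is unknown, at 6.7% of the planned completers each. The stated power stands, and no bias in the 6-of-15 criterion is asserted. The point should be fixed because following the inclusion list as printed can enrol people whom the stated population excludes.

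**What to change.** - Reconcile the Number of subjects paragraph and the Inclusion Criteria list to one severity rule, worded identically in both. The sponsor and investigator should decide whether an IGA route is kept.
- If it is kept, name its grades in words consistent with the moderate-severe label, not by number alone.
- Define one IGA scale, with its direction and a label for every grade. Use it in the Inclusion Criteria, Disease status assessment, Primary Outcomes and the photograph score.
- Report how many subjects, if any, entered on IGA alone, with their baseline EASI.

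The cost is a short amendment to the eligibility and scale definitions, with no new procedures. If the IGA route is removed or narrowed, the eligible pool may shrink somewhat; the protocol gives no basis for estimating by how much.

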**Exclusion Criteria:**

- As determined by the study doctor, a medical history that may interfere with study objectives (cancer, chronic illness)
- Known allergy to tetracycline
- Hand eczema only (no body involvement).
- Subjects with a systemic infection requiring a course of systemic antibiotics or antivirals within the last 2 weeks
- Unstable AD or any consistent requirement for systemic immune-modulant Rx (e.g. systemic steroids, phototherapy, Cyclosporine)
- History of use of biologic therapy (including intravenous immunoglobulin)
- Recent or anticipated concomitant use of systemic therapies that might alter the course of AD
- Recent or current participation in another research study
- Females who are breastfeeding, pregnant, or anticipate becoming pregnant during the study time frame
- Subjects with a history of keloid formation
- History of lidocaine, epinephrine or Novocain allergy
- History of allergy to tape or other adhesive materials

**3. METHODS AND PROCEDURES**

**Study Design.** We will perform a 6 weeks, pilot, investigator-initiated, single-center, open-label clinical study to determine the effect of NANODOX® 1% hydrogel in adult AD patients. The study will be conducted in the UF Health Dermatology Department - Springhill.

Subjects that voluntarily agreed to participate will be consented and enrolled in the study. Qualified subjects will be required to come to UF Dermatology Clinic for at least four visits, approximately 2 weeks apart, with an optional pre-screening (up to 28 days +/- 2 prior to V1) visit if washout is needed and/or to allow subjects to be enrolled in pre-established enrollment dates. Each visit will last approximately 30-60 minutes.

Subjects will be asked to apply NanoDOX® Hydrogel 1% once daily at bedtime for total of four weeks (or until complete clearance) on the chosen target eczematous and adjoining clinically normal (perilesional) area (to cover an area of the size of an index card). NanoDOX® Hydrogel 1% will be provided to the patient in single dose package containing 1.5 cc of hydrogel (equal to 15mg Doxycycline) which is enough to cover a skin area of the size of an index card. Alchem will provide drug for the study at no cost. Of note, for systemic use doxycycline is used at concentration from 100 mg (antimicrobial) twice daily to 40 mg (anti-inflammatory) daily for periods ranging from 14 days to several months. We included non-lesional/perilesional skin to evaluate the safety (e.g. irritant or toxic effects) of the compound on atopic skin, as those subjects have a lower irritancy threshold as is compared to non-atopic subjectsxii. Also, skin barrier impairment (e.g. increase water loss & increase pH) can be already detected in normal

appearing skin in AD subjects. It is our hypothesis that by normalizing the proteases activities, treatment with NanoDOX® Hydrogel will normalize skin barrier integrity.

Subjects that are on any topical treatment (e.g. steroids, calcineurin antagonist) will be asked to discontinue the use of those medications only in the selected area for one week before starting the study (washout period). During the study, subjects will be allowed to stay on anti-histamine and any topical treatment (except for the treatment area) on a stabilized dose, and expect to maintain this dose throughout the study. In case of acute flare (e.g. intense itch, increase redness, pain or oozing) in the treatment area subjects will be allowed to use rescue medication (e.g. topical steroid or calcineurin inhibitors that they used before the study) under the PI supervision. The need for rescue topical treatment will be monitored and recorded during the study and it will be used as an indication of the efficacy of the treatment.

Study Design: Evaluation of NanoDOX Hydrogel 1% in AD subjects.				
(Vp)	V1	V2	V3	V4
Pre-Screening <28days	Day 0	Day 14 +/- 2	Day 28 +/- 2	Day 42 +/- 5
Clinical & itch score, Skin barrier, photographs	X	X	X	X
Swab, Blood & Skin biopsy	X		X	

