### **Secondary Outcomes:**

1. Improvements of itch score (0-5 scale) in lesional skin, before and after treatment at each time point. 2. Will evaluate Staphylococcal Aureus rate of colonization (positive or negative), difference in number of growth (0 to 3+++ ) and antibiotic sensitivity pre and post treatment. Doxycycline could have an effect on AD lesions just by reducing the Staphylococcal Aureus colonization. By integrating these findings with clinical outcomes, drug penetration and molecular changes we will be able to start to address this question. 3. Improvement of barrier function in non-lesional (normal appearing) and lesional skin pre and post treatment (V1 to V3). We will expect that clinical improvement parallels with improvement of barrier function, such as reduced TEWL, increased stratum corneum hydration and reduced pH in active treatment areas. On the other hand, worsening of the measurement will suggest damaging effect of the treatment on the skin, which could be indication of subclinical irritation induced by the treatment and/or vehicle.

The purpose of this study is a proof of concept. We are adopting a similar strategy to Phase II cancer trials that seek a clinically significant response. Using exact binomial methods, we shall obtain point and interval estimates for the fraction of subjects who respond as (a) At least EASI 50% by visit 2 or 4 and (b) At least EASI 75% by visit 2 or 4. We shall also tabulate the IGA score from baseline to visit 4. We would consider 6 or more responses (a) in 15 subjects as promising. The probability of declaring a promising result when the true response rate is 60% or higher is over 96% (power).

Side effects and baseline characteristics will be tabulated qualitatively. The blinded pre-vs post evaluation will be analyzed for IGA scores by the Wilcoxon sign-rank test.

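### The EASI50/EASI75 response rule has no rescue condition, so a subject rescued on the target area can count toward the 6-of-15 threshold

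*Combined protocol and SAP*

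**What the plan says.** **Rescue.** Section 3 (Study Design) provides that, in an acute flare, "in the treatment area subjects will be allowed to use rescue medication (e.g. topical steroid or calcineurin inhibitors that they used before the study"). The principal investigator supervises this use. Need for rescue is to be recorded, and "it will be used as an indication of the efficacy of the treatment". How it will be used is not stated.

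**What is scored.** The Primary Outcomes in Section 5 take "Improvements rate of IGA and EASI score in lesional skin treated with" the study gel, so rescue would go onto the skin being scored. Under Study procedures & methods, EASI has two versions: "it is recorded for targeted treatment areas as well as four regions of the body". The same paragraph adds: "Data will be reported as percent change in EASI score from baseline and each visit".

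**Response and decision.** The statistical paragraph under Secondary Outcomes estimates "the fraction of subjects who respond as (a) At least EASI 50% by visit 2 or 4", with (b) the same for EASI75. It does not name the EASI version. It then says: "We would consider 6 or more responses (a) in 15 subjects as promising". The power statement is: "The probability of declaring a promising result when the true response rate is 60% or higher is over 96% (power").

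None of these places makes a rescued subject a non-responder, sets aside scores taken after rescue, or plans a sensitivity analysis for rescue.

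**The concern.** Two parts of the plan can classify the same subject in opposite ways. Section 3 treats needing rescue as information about how well the gel works. Section 5 can score that subject as a success of the gel, because only the percentage fall from baseline matters. The plan does not say which governs.

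The omission can only raise the count, since a post-rescue improvement is credited to the gel. The study is open-label with a single arm, so no comparison group exists against which to judge a rescue-assisted response. Visit 4 (Day 42) falls about two weeks after the four weeks of dosing, so rescue in that interval can still affect a score that counts. The 6-of-15 threshold is the study's only stated efficacy decision rule, and a single subject can decide it. If the classification is left open, it will be chosen once the data are visible.

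**Working it through.** **1. The plan's own figure.** Inputs from Section 5: n = 15, threshold 6, true rate 60%. With X ~ Bin(15, 0.60), P(X ≥ 6) = 0.966. This agrees with the stated power of over 96%. Thresholds of 5 and 7 would give 0.991 and 0.905, so the rule is indeed 6 or more.

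**2. Effect of one subject, with no assumed rates.** Exact (Clopper–Pearson) 95% intervals:

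| Responders | Rate | 95% CI | Label |
|---|---|---|---|
| 5/15 | 33% | 12–62% | not promising |
| 6/15 | 40% | 16–68% | promising |

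One rescue-assisted responder crosses the threshold, although the two intervals are nearly the same.

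**3. Sensitivity of the chance of reaching 6/15.** The documents give no rescue rate, no success rate after rescue and no uninteresting response rate, so every input here is assumed. Let p be the unaided response rate, r the share of the remaining subjects rescued on the target area, and e the share of those who then reach EASI50. The apparent rate is q = p + (1 − p)·r·e, and the result is P(X ≥ 6) with X ~ Bin(15, q). With p = 0.20:

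| r | e | q | P(≥ 6/15) |
|---|---|---|---|
| 0 | – | 0.20 | 0.061 |
| 0.05 | 0.25 | 0.21 | 0.075 |
| 0.10 | 0.25 | 0.22 | 0.090 |
| 0.10 | 0.50 | 0.24 | 0.127 |
| 0.20 | 0.50 | 0.28 | 0.222 |
| 0.30 | 0.50 | 0.32 | 0.339 |

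For example, r = 0.20 and e = 0.50 give q = 0.20 + 0.80 × 0.20 × 0.50 = 0.28.

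**4. Which EASI.** On a four-region score at the Section 2 entry threshold of 10, EASI50 needs a fall of 0.5 × 10 = 5 points. The treated area is about the size of an index card, so rescue confined to it could contribute little to such a fall. On a target-area score, rescue acts on the whole of what is measured.

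**5. Power if rescue counts as non-response.** If 60% is already a rescue-free rate, power stays at 0.966. If instead 60% applies only to subjects who are not rescued, and a share s of all subjects is rescued, then q = 0.60 × (1 − s):

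| s (assumed) | q | Power |
|---|---|---|
| 0.10 | 0.54 | 0.911 |
| 0.20 | 0.48 | 0.810 |
| 0.30 | 0.42 | 0.657 |

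These are rough lower bounds, because they give no credit for a visit 2 response achieved before any rescue. Note that s is a share of all subjects, whereas r in step 3 is a share of unaided non-responders, so the two tables should not be compared row by row.

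**The case against.** The strongest reply is that this is an unwritten classification rule in a 15-subject pilot, not hidden data. Rescue is to be recorded, so rescued responders could be listed one by one. A reader might infer that rescue effects would be invisible in the results. The documents do not support that: the overlap can be seen, and only the unaided outcome of a rescued subject is unknowable. Vehicle effect and spontaneous improvement are harder to isolate in this design than rescue is.

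The route is also narrow. A subject must flare in the treated area, be rescued, and then be at least 50% below Day 0 at visit 2 or 4. Nothing in the documents says how often that would happen. A reader might take the 34% in the working as the expected inflation; it is one corner of an assumed grid, and milder inputs give 7–9%. The move from 5/15 to 6/15 would likewise follow from any single misclassification.

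Nor is the 6-of-15 threshold the only decision rule in the protocol. Section 4 has a separate safety stopping rule, and promising is a proof-of-concept label with no action attached.

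Finally, counting observed scores and tabulating rescue is another defensible choice. All of this limits the size of the point. It does not supply the missing rule: using rescue as an indication of efficacy does not alter who is a responder in Section 5.

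**Conclusion.** The gap is real and should be fixed. As written, a subject rescued on the target area who then meets EASI50 against Day 0 at visit 2 or 4 counts toward the promising threshold. The direction of bias is upward, and the point applies mainly to the target-area score that the Primary Outcomes indicate.

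Its size cannot be determined from the documents. What is certain is that one such subject can change the label. At an assumed 20% unaided rate, the chance of at least 6/15 moves from 6% to about 7–9% (5–10% of non-responders rescued, 25% success) or to 13–34% (10–30% rescued, 50% success).

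A reader might also infer that the power statement is wrong. It is not: it reproduces. What it lacks is a statement of whether the 60% is free of rescue. Confidence is high on the omission and low on its practical impact.

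**What to change.** Add to the statistical paragraph in Section 5:

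- Responses (a) and (b) use the target-area EASI.
- A subject who has used rescue medication on the target area is a non-responder for (a) and (b) at every visit on or after first use. A visit 2 response before any target-area rescue still counts.
- The count ignoring rescue is reported as a sensitivity analysis.
- The number of subjects rescued and the timing of first use are tabulated beside both counts.
- The 60% behind the power figure is a rescue-free response rate.

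In the rescue recording that Section 3 already requires, capture the site (target area or elsewhere) and the date of first use. The medication reviews at visits 2, 3 and 4 do not specify either, and topical treatments are allowed outside the treatment area.

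**Cost.** A few sentences and two data fields, with no new visit or procedure. Access to rescue is unchanged; only the analysis classification is defined. The rule is conservative: some rescued subjects might have responded unaided. A subject who first reaches EASI50 at visit 3 and is rescued after dosing ends would not count, because (a) and (b) name only visits 2 and 4. Power is unaffected if 60% is rescue-free. Otherwise the 91%, 81% and 66% in the working (10%, 20% and 30% of subjects rescued) are a rough lower bound. The sensitivity count will show how many responses the rule removes.
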